### **8.3 Vital Signs**

Summary tables will be presented for vital sign data, including systolic blood pressure (mmHg), diastolic blood pressure (mmHg), body temperature (°C), respiratory rate (bpm), pulse rate (bpm), height, and weight for subjects in the safety population. Observed results at the scheduled visits and changes from baseline to post-baseline visits will be presented. All vital sign data by subject will be presented in a listing.

### **8.4 Physical Examination**

The abbreviated physical examinations will be conducted at Screening and EOT visits. A general physical exam will also be conducted at the 6-Week FU for all subjects, except VVC subjects. The abbreviated physical examination comprises a routine medical examination including general appearance, skin, eyes, heart, chest, and abdomen.

All abbreviated physical examinations will be classified as Normal, and Abnormal at baseline. Post-baseline examinations will be classified as “Changes from baseline” or “No change from baseline”. This categorical data will be summarized with the frequency and percentage of subjects by body system at each scheduled visit.

Any abnormalities noted during the physical examination and associated with adverse events, will be presented in a listing for all subjects.

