9.0 Study Endpoints

9.1 Primary Endpoints

The primary endpoints listed below apply to all eligible fungal diseases:

- Efficacy as measured by the percentage of subjects with Global Response at TOC for VVC (Day 17), CMC (EOT or Day 84), CPA (EOT or Day 90) and ABPA (EOT or Day 90) (whichever comes first) and at EOT for all other diseases as determined by a DRC
- Safety as measured by: physical examination, vital signs, AEs, and laboratory tests

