Note: For subjects who are suspected to have a relapse of infection during the study follow-up period, evaluations relevant to the signs and symptoms of infection should be performed before starting non-study antifungal therapy. The results of these studies should be documented on the eCRF. Subjects who have a recurrence after TOC (VVC) or EOT (all other diseases), may be considered for re-enrollment upon discussion with the Sponsor.

The signs and symptoms of fungal infection include, but are not limited to, the following:

- General signs and symptoms:
 - Fever, defined as oral temperature $\geq 38.3^{\circ}\text{C}$ ($\geq 101^{\circ}\text{F}$) on one occasion or $>37.8^{\circ}\text{C}$ ($>100^{\circ}\text{F}$) on two measurements at least 4 hours apart
 - Clinically significant hypothermia $<36^{\circ}\text{C}$ ($<96.8^{\circ}\text{F}$)
 - Hypotension (systolic blood pressure <90 mmHg or a >30 mmHg decrease below normal baseline)

- Tachycardia
- Local signs and symptoms of inflammation
- Disease-specific signs and symptoms:
 - OPC: White patches or plaques on the tongue and other oral mucous membranes, redness or soreness in the affected areas, difficulty swallowing, cracking at the corners of the mouth (angular cheilitis)
 - EC: White plaques and/or ulcers on the lining of the esophagus or narrowing of the lumen, pain when swallowing, difficulty swallowing, heartburn
 - CMC: Extensive scaling, skin lesions, thickened nails
 - Other signs and symptoms of candidiasis and other fungal diseases, as applicable

Subjects who are discharged from hospital during ibrexafungerp therapy will record their signs and symptoms daily on subject diaries, and the signs and symptoms will also be assessed by the site staff at the study visits. The site will assess whether the signs and symptoms recorded on the subject diary are related to the fungal disease.

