14.3.2 General Physical Examination

A general physical exam will be done at Screening and EOT. A general physical exam will also be conducted at the 6-Week FU for all subjects, except VVC subjects. The physical examination will include an abbreviated assessment of general appearance, skin, eyes, heart, chest and abdomen.

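### The physical-examination safety table (SAP 8.4) records change without direction or baseline status, so alone it cannot separate new abnormalities from healing where baseline abnormality is common

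*SAP*

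**What the plan says.** Protocol 9.1 makes physical examination part of the primary safety endpoint: "Safety as measured by: physical examination, vital signs, AEs, and laboratory tests". Protocol 14.3.2 sets the content: "The physical examination will include an abbreviated assessment of general appearance, skin, eyes, heart, chest and abdomen". SAP 8.4 repeats those body systems. The examination is done at Screening and EOT, and at the 6-Week FU for everyone except VVC subjects.

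SAP 8.4 then uses two different scales. For baseline: "All abbreviated physical examinations will be classified as Normal, and Abnormal at baseline". For later visits: "Post-baseline examinations will be classified as “Changes from baseline” or “No change from baseline". The planned output is: "This categorical data will be summarized with the frequency and percentage of subjects by body system at each scheduled visit". The one further output that 8.4 names is a listing: "Any abnormalities noted during the physical examination and associated with adverse events, will be presented in a listing for all subjects".

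Other safety data are handled differently. SAP 8.2 classes laboratory values as Low, Normal or High and shows shifts against baseline. SAP 8.3 gives vital signs as observed values and changes from baseline.

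**The concern.** A class that records change but not its direction suits a population that starts out healthy, because any change is then for the worse. These subjects enter with active fungal disease, and some of the examined systems are where that disease shows. Protocol 14.2.1 gives an example: "CMC: Extensive scaling, skin lesions, thickened nails". CPA, ABPA and IPA are lung diseases. SAP 7.1.1 groups invasive candidiasis by sites that include pleural/pulmonary, intraabdominal/pelvic and soft tissue/wound. Nothing in either document keeps signs of the baseline infection out of the general examination.

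A finding that clears on treatment is thus counted as a change in a safety table, beside a finding that is new. The study has a single arm, so no control column shows how much change to expect from recovery. At stake is whether the specified summary of a named safety component can be read on its own.

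**Working it through.** The documents give no figure for examination findings, so there is nothing to reproduce. The check is a reading of the text, followed by a bound.

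**1. What each class contains under SAP 8.4**

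| Baseline | Course | Class |
|---|---|---|
| Normal | new abnormality | changed |
| Normal | stays normal | unchanged |
| Abnormal | improves or resolves | changed |
| Abnormal | worsens | changed |
| Abnormal | persists | unchanged |

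Three courses share the changed class and two share the unchanged class. Baseline status would separate the first row from the third and fourth. SAP 8.4 classifies baseline status but does not say that the post-baseline counts will be split by it.

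**2. When the table is read.** The post-baseline examinations are at EOT and, except for VVC, six weeks later. For most diseases EOT is also the primary efficacy time point (SAP Table 5), so resolved findings would be expected at the visits being tabulated.

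**3. How far the table limits the answer.** For one body system and visit, let B be the number abnormal at baseline and C the number classed as changed. Assume that everyone is examined and that a subject normal at baseline can change only for the worse. The number with a new or worse finding then lies between

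max(0, C − B) and C,

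an interval of width min(B, C).

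The following counts are assumed only to show how the bound behaves. N = 220 is the planned enrolment and C = 40, so 40/220 = 18.2% are classed as changed.

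- B = 44: max(0, 40 − 44) = 0, so 0 to 40 subjects (0% to 18.2%).
- B = 10: 40 − 10 = 30, so 30 to 40 subjects (30/220 = 13.6% to 18.2%).
- B = 0: exactly 40 subjects (18.2%).

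The table is fully informative when nobody is abnormal at baseline, nearly so when few are, and uninformative about harm once B reaches C.

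**4. What a split by baseline status would add.** Write C = C_N + C_A for changes from Normal and from Abnormal. New abnormalities in subjects normal at baseline are then C_N exactly. New or worse findings lie between C_N and C_N + C_A. The width is C_A, which cannot exceed min(B, C), so the interval is never wider than before. What remains uncertain is confined to changes from Abnormal, and only a recorded direction can resolve it.

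**The case against.** The strongest reply is that no safety signal depends on this table.

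- Protocol 16.1 counts any unfavourable sign as an adverse event. Signs of the studied disease are left out only if they do not worsen and are no more severe than expected. A new or worsening finding therefore belongs in the tables of SAP 8.1, by term, severity, relatedness and seriousness. SAP 8.2.2 separately summarizes liver-test elevations. Healing enters none of these.
- The AE-linked listing is not the only other output. Protocol 18.6.2 promises listings of all safety variables, and SAP 8 promises subject listings behind the tables. Direction may be recoverable from them if it was recorded.
- The overlap with disease is partial. Disease-site signs have their own targeted examination (Protocol 14.2.1). The abbreviated examination names no oropharyngeal, oesophageal or vulvovaginal assessment, so OPC, EC and VVC signs largely fall outside it.
- A cross-tabulation is not ruled out, because SAP 11 keeps the list of tables outside the SAP.
- The safety analyses are descriptive, and no test or decision rule uses this table.

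All of this stands, and it limits how much the point matters. It does not change how 8.4, followed as written, counts a change.

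A reader might go further and infer that the table supports no safety statement in either direction, or that harm is being hidden. The documents do not support either inference. The ambiguity arises only in subjects abnormal at baseline in that system, and harm has its own route.

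A reader might also try to size the effect from the preliminary result in Protocol 7.1, where 11 of 20 subjects had a Complete or Partial Global Response. That is not an examination resolution rate. Partial response is improvement and not resolution, the composite includes mycology and radiology, and those subjects included esophageal and oropharyngeal disease and spondylodiscitis, which this examination would largely not show. No source is given for baseline abnormality or new-finding rates either, and the 8.4 table is by body system and not pooled.

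**Conclusion.** The point holds in a limited form. As specified, the 8.4 summary pools resolution, worsening and new abnormality in one class. By itself it cannot separate new findings from healing in body systems where many subjects are abnormal at baseline; skin in CMC and chest in pulmonary disease are the plausible cases. Where few are abnormal at baseline, the table remains readable.

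Materiality is modest, because adverse events and listings still capture harm. No numerical size can be given from the documents, and the counts in the bound are illustrative only. The conclusion rests on two readings: that the absence of any stated split by baseline status means none is currently specified, and that signs of the baseline infection may be recorded in the general examination because nothing excludes them.

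**What to change.** In SAP 8.4, present the post-baseline class cross-tabulated by baseline Normal/Abnormal for each body system and scheduled visit, in line with the laboratory shift tables in SAP 8.2. Report changes from Normal as new abnormalities.

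For changes from Abnormal, the wording depends on the eCRF, which the documents do not describe:

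- If direction is recorded, split them into improved/resolved and worsened.
- If it is not, add a footnote that their direction is unknown and that they are not to be read as evidence of harm.

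The cost is a short change of SAP wording and one revised table shell. Baseline status is already classified under 8.4, so the basic split needs no new data. The drawback is one extra table dimension with small cells, more so if the table is also broken down by disease category. The improved/worsened split is available only if the direction field exists.

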### **8.5 Mycological Testing**

For VVC subjects, samples for fungal culture will be collected at Screening, EOT, TOC, and 25-Day FU. Additional samples will be obtained, if applicable, at Baseline/Day 1 and at any unscheduled visits. For symptomatic subjects, samples will also be collected at the 35-Day FU visit. For all other fungal disease subjects excluding VVC, mycological samples will be obtained for all subjects at Screening and/or Baseline/Day 1 (prior to treatment), and as applicable for each subject and fungal disease while on therapy. In addition, samples will be collected at the per-protocol visits displayed in [Table 3](#).

The KOH testing results will be classified as Positive (Yeast Only), Positive (Yeast and other pathogens), Negative (Yeast and other pathogens), and Positive (Other pathogens only). All other testing results will be classified as Positive or Negative. This categorical data will be summarized with the frequency and percentage of subjects at the scheduled post-baseline visits.

All by-subject mycological testing will be presented in a listing.

## **9. Pharmacokinetics**

A detailed description of PK parameters and analysis will be presented in a separate pharmacokinetics report.

## **10. Interim Analysis and Supplemental Analysis**

No interim analysis is planned for this study.

## **11. Tables, Listings, and Figures**

A list of tables, listings, and figures will be maintained outside of this document and may be amended as needed.
